However, these previous rehabilitation trials have shown that such improvements are often selective only to the task which has been paired with VNS. Specifically, in rats, motor behaviors paired with implanted VNS following stroke demonstrated selective increases in the size of the motor representations within the motor cortex for trained behaviors, while motor representations for untrained tasks or tasks performed without VNS remained relatively unchanged [19]. Human and animal models of tinnitus rehabilitation involving selective pairing of VNS with tones outside of the tinnitus white noise perceptual range resulted in significant reductions in the perception of tinnitus for up to three months [20-21]. In stroke rehabilitation, one of the most notable hindrances to motor recovery is the persistence of

maladaptive upper and lower limb flexor synergy patterns. Upper extremity flexor synergy is characterized by a fixed pattern of scapular retraction, shoulder abduction/external rotation, elbow/wrist/finger flexion, and wrist supination, resulting a 'curling in' of the arm towards the body with a rigid, closed hand. It is caused by damage to the corticospinal tract (CST), and subsequent upregulation of interneuron spinal networks and other descending spinal pathways, ultimately resulting in movement limitations, which are greatest for extensor movements [22]. Given the apparent task-selectivity of VNS training, current delivered only during extensor movements of a motor therapy task might lead to more efficient recovery of arm function after stroke.

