7. ELIGIBILITY CRITERIA

- Describe the characteristics of the subject population, including their anticipated number, age, ranges, sex, ethnic background, and health status. Identify the criteria for inclusion or exclusion of any subpopulation.
- Explain the rationale for the involvement of special classes of subjects, such as fetuses, pregnant women, children, prisoners or other institutionalized individuals, or others who are likely to be vulnerable. You cannot include these populations in your research, unless you indicate such in the protocol
- Similarly, detail exclusionary criteria: age limits, special populations (minors, pregnant women, decisionally impaired), use of concomitant medications, subjects with other diseases, severity of illness, etc.

Inclusion Criteria:

- Individuals between 18 and 85 years of age
- First single focal unilateral supratentorial ischemic stroke with diagnosis verified by brain imaging (MRI or CT scans) that occurred at least 6 months prior
- Cognitive function sufficient to understand the experiments and follow instructions (per interview with Speech Pathologist or PI)
- Fugl-Meyer assessment 12 to 44 out of 66 (neither hemiplegic nor fully recovered motor function in the muscles of the shoulder, elbow, and wrist).

Exclusion Criteria:

- Botox treatment within 3 months of enrollment
- Fixed contraction deformity in the affected limb
- Complete and total flaccid paralysis of all shoulder and elbow motor performance
- Prior injury to the vagus nerve
- Severe dysphagia
- Introduction of any new rehabilitation interventions during study
- Individuals with scar tissue, broken skin, or irremovable metal piercings that may interfere with the stimulation or the stimulation device
- Highly conductive metal in any part of the body, including metal injury to the eye; this will be reviewed on a case by case basis for PI to make a determination
- Pregnant or plan on becoming pregnant or breastfeeding during the study period
- Significant arrhythmias, including but not limited to, atrial fibrillation, atrial flutter, sick sinus syndrome, and A-V blocks (enrollment to be determined by PI review)
- Presence of an electrically, magnetically or mechanically activated implant (including cardiac pacemaker), an intracerebral vascular clip, or any other electrically sensitive support system; Loop recorders will be reviewed on a case by case basis by PI and the treating Cardiologist to make a determination

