10. ENDPOINTS

- *Describe the primary and secondary study endpoints*
- *Describe any primary or secondary safety endpoints*

The primary measure of treatment efficacy will be an increase in EMG activation peak amplitude for upper extremity extensor muscles of at least 10%. The secondary measure of treatment efficacy will be an improvement in Upper Extremity Fugl Meyer score of at least 3 points (out of 66).

The primary safety endpoint will be any serious adverse events of suspected relationship with the tVNS investigational device. Any serious adverse events will be reported to the PI, research team, and IRB immediately for determination if the study should be discontinued. However, given that there were no serious adverse device effects of implanted VNS in individuals with stroke [8], it is anticipated that transcutaneous auricular vagus nerve stimulation will pose an even lower risk.

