During planar robot therapy, the patient's hand and wrist are held in a rigid support affixed to the robotic arm, and the patient must reach towards points in space that correspond to the positions of the targets on a screen. Throughout each therapy session, the participant completes a series of flexions, extensions, and rotational movements across the elbow and shoulder joints. If a limb is initially paralyzed, the robot will move it passively, but as motor function returns, the robot will require the patient to initiate progressively more voluntary movement. In this way, the robot safely delivers reproducible movement without tiring and can render the level of training intensity required to alter impairment.

Robotic therapy has been established as a safe and effective tool for upper limb motor recovery after stroke, and is presently a recommended intervention by the American Heart Association [1].

Transcutaneous auricular vagus nerve stimulation (tVNS)

Electrical auricular stimulation will be accomplished using either the Roscoe Medical Transcutaneous Electrical Nerve Stimulation (TENS) 7000 device paired

with ear clip electrodes available from Lhasa Ohms or an Auricular Branch Vagus Nerve Stimulation device co-designed by the CBEM team and fabricated by the MIDI Product Development Corporation. The study will only use one device throughout its conduct for all study participants since using multiple devices will create unnecessary variability. If the Auricular Branch Vagus Nerve Stimulation device from the MIDI Product Development Corporation is received prior to the anticipated study start date and passes internal reviews for design, comfort, and performance, the study will use the Auricular Branch Vagus Nerve Stimulation device from the MIDI Product Development Corporation for the entirety of the study for all subjects. If it is not received by the anticipated start date of this study, the study will utilize only the Roscoe TENS 7000 unit for the entirety of the study for all subjects.

Study Procedure:

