Electrical activity of the muscle will be differentially recorded during tVNS sessions using a bipolar electrode montage placed on the belly of the muscle. Recordings will be made from the biceps and triceps brachii, pectoralis major, rhomboideus, and/or the deltoids, which are some of the important muscles responsible for flexion and extension of the shoulder and elbow.

Randomization

Subjects will be stratified by established clinical impairment levels based upon admission Upper Extremity Fugl Meyer scores (low function <23 & moderate function 23-44) such that there are an equal number of low and high functioning patients in each treatment group. Subjects will then be randomized to either the active or sham tVNS group [28]. Assignment will be predetermined by a randomized assignment list, created prior to the enrollment of the first subject by an investigator from the CBEM team who is not directly involved in subject treatment. There will be concealed allocation of treatment assignment such that investigators involved in subject screening, consent, and clinical scoring will be blinded to treatment condition.

Blinding

This will be a double-blind pilot study in which subjects will be randomly assigned to either the sham or active tVNS conditions. Subjects will be told that they have a 50-50 chance of receiving either active or sham stimulation, but they will not be told which condition they receive. Additionally, the assigned clinical evaluators will remain blinded to condition. For each study session, stimulation condition will be programmed into the device by the RA or members of the CBEM team who are not performing clinical measures.

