12. STATISTICAL ANALYSIS

- *Describe how your data will be used to test the hypotheses.*
- *State clearly what variables will be tested and what statistical tests will be used.*
- *Include sample size calculations.*
- *If this is a pilot study, state which variables will be examined for hypothesis generation in later studies.*

For our primary outcome measure, we will investigate whether tVNS paired in a closed loop with robotic therapy changes peak amplitude EMG activation in muscle groups along the shoulder and elbow. We hypothesize that upper extremity flexor synergy will be significantly improved when active tVNS is applied during extensor movements as compared to a sham condition, and will lead to an increase in EMG peak activation at the triceps brachii (elbow extensor muscle). This will be examined with a 2x3 ANOVA with condition (active stimulation vs. sham) and time (peak amplitude of EMG activation during extensor movements at admission, discharge, and follow-up) as factors.

For our secondary outcome measure, we will test whether active tVNS during extensor movements paired in a closed loop with intensive robotic intervention (9 sessions) significantly improves upper extremity motor function as compared to sham tVNS paired with intensity-matched robotics. This will be examined with a 2x3 Friedman ANOVA with condition (active vs. sham tVNS) and time (upper extremity fugl meyer score at admission, discharge, and 3 month FU) as factors.

Since this is a pilot study, there are presently no data from which we can derive a power calculation. However, we propose to enroll 36 subjects, in order to achieve a target of at least fifteen subjects per treatment group and also allow for a 10-15% drop out rate. In our extensive past experience with upper limb hemiparesis rehabilitation studies, 10-15 subjects per treatment group is required at minimum to capture a measurable treatment response. Additionally, two other early pilot studies investigating post-stroke upper limb motor rehabilitation combined with VNS found a significant improvement in motor performance with nine and fourteen subjects per treatment group (e.g. sham and active VNS), respectively [8 & 41].

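### Section 10 defines primary efficacy as a 10% rise in extensor EMG with no sham comparison, level or noise floor, so measurement error alone can meet it

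*Combined protocol and SAP*

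**What the plan says.** **Endpoint.** Section 10 gives the primary measure of efficacy as "an increase in EMG activation peak amplitude for upper extremity extensor muscles of at least 10" percent. It names no comparator, visit, reference baseline, minimum detectable amplitude or reason for choosing 10%. It does not say whether the figure applies to each patient or to a group mean.

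**Analysis.** Section 12 tests the primary outcome differently: "This will be examined with a 2x3 ANOVA with condition (active stimulation vs. sham) and time" (admission, discharge, follow-up). The variable is peak EMG amplitude during extensor movements, and the triceps is named as the muscle expected to change. The 10% does not appear there. No variability or repeatability of the EMG measure is given, and the section states that there are no data for a power calculation.

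**Who may enter.** Section 7 requires "Fugl-Meyer assessment 12 to 44 out of 66 (neither hemiplegic nor fully recovered motor function in the muscles of the shoulder, elbow, and wrist") and excludes "Complete and total flaccid paralysis of all shoulder and elbow motor performance". Neither criterion sets a minimum for triceps or other extensor activity. Section 3 describes "movement limitations, which are greatest for extensor movements". Section 11 stratifies randomization by Fugl-Meyer score ("low function <23 & moderate function 23-44") and schedules two to three baseline measurement periods. The first aim in Section 4 concerns EMG during unassisted, gravity-eliminated movement.

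**The concern.** A relative change of 10% is small beside the visit-to-visit variation that a surface EMG peak could plausibly show. If Section 10 is applied as written, the trial could report that the active arm, or a proportion of its patients, met the primary efficacy measure when nothing but repeat-measurement error had occurred. Sham patients would meet it at the same rate, but the criterion does not ask about them.

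The problem may be sharper in patients with little triceps signal, because a percentage change divides by a small number. The criteria permit such patients: someone with some shoulder or flexor movement and a weak triceps can satisfy both the Fugl-Meyer range and the paralysis exclusion.

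The trial would then have two possible definitions of success, the 10% rise and the ANOVA, with no rule for which decides. A pilot meant to guide later work should not leave that choice until the results are known.

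**Working it through.** **The plan's own figures.** The 10% threshold has no derivation to reproduce. The arm size used below does: at least 15 per group, 30 in all, inflated for 15% dropout gives 30 / 0.85 = 35.3, rounded up to the planned 36. At 10% dropout it gives 30 / 0.90 = 33.3, rounded up to 34.

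**Assumptions.** The documents give no EMG amplitude or repeatability, so every CV, SD and microvolt value below is assumed. True change is zero throughout.

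**1. Error proportional to signal, per-patient reading.** Let the within-patient error be lognormal with s² = ln(1 + CV²), and let the baseline be the geometric mean of k readings. Then

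P(post/pre ≥ 1.10) = 1 − Φ( ln 1.10 / (s·√(1 + 1/k)) ), with ln 1.10 = 0.0953.

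For CV 10% and k = 1: s = 0.0998 and 0.0953 / (0.0998 × 1.414) = 0.676, so P = 25%. For CV 20% and k = 1: s = 0.198 and 0.0953 / (0.198 × 1.414) = 0.340, so P = 37%.

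| Assumed CV | One baseline | Three baselines averaged |
|---|---|---|
| 5% | 9% | 5% |
| 10% | 25% | 20% |
| 20% | 37% | 34% |
| 30% | 41% | 39% |
| 50% | 44% | 43% |

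These rates do not depend on the patient's amplitude. Averaging the lead-in recordings helps only modestly once the CV is 10% or more.

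**2. Constant absolute error, per-patient reading.** With baseline b and error SD σ on each of two readings,

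P(y₁ ≥ 1.1·y₀) = 1 − Φ( 0.1·b / (σ·√(1 + 1.1²)) ), with √2.21 = 1.487.

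For b = 10 and σ = 5: 1 / 7.43 = 0.135, so P = 45%. For b = 100 and σ = 5: 10 / 7.43 = 1.345, so P = 9%.

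| Baseline | σ = 3 | σ = 5 | σ = 10 |
|---|---|---|---|
| 10 microvolts | 41% | 45% | 47% |
| 100 microvolts | 1% | 9% | 25% |

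Only under this error model does the false-pass rate depend on baseline signal. The normal model is rough at b = 10 and σ = 10, where about 16% of readings would be negative.

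**3. Within-arm reading, 15 patients.** For the geometric mean of 15 post/pre ratios under proportional error, divide the SD of the log ratio by √15. The chance of reaching 1.10 is 0.4% at CV 10%, 9% at CV 20% and 29% at CV 50%.

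The scale also matters. Take constant error, two patients at 10 microvolts and thirteen at 100, with values floored at 1 microvolt. In simulation, the mean of the individual percentage changes reaches 10% in about 8% of null trials at σ = 3 and about 25% at σ = 5. The ratio of the post and pre arm means does so in under 1%.

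**4. The planned comparison.** The 2x3 condition-by-time interaction on raw amplitude was simulated under no effect. Assumptions: 20,000 trials, 15 per arm, about half of each arm at one tenth of the others' mean amplitude, CV 15 to 50% in those patients and 15% in the rest. The false-positive rate was 3.9 to 4.6%. The share of patients showing a 10% rise was equal in the two arms, at 33 to 39%. In the same trials, the active arm's mean amplitude taken alone rose by 10% or more in about 11 to 12%.

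**The case against.** The strongest reply is that the trial will be judged on Section 12, not on the sentence in Section 10. The planned test is randomized, double-blind and sham-controlled, and it uses amplitude rather than percentage change. Error is the same in both arms, so it costs power and does not create a treatment effect. On raw amplitude, low-signal patients carry little weight. This stands, and step 4 agrees with it. A reader might infer that the primary analysis credits improvement where none exists; the documents do not support that.

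A reader might also infer that the trial will enrol patients with almost no extensor activity, in whom a 10% change is only noise. That goes too far. The Fugl-Meyer range of 12 to 44 is a separate entry requirement. Section 3 speaks of limited extensor movement, not absent extensor EMG. The Section 11 remark "If a limb is initially paralyzed, the robot will move it passively" describes how the robot works in therapy, whereas the EMG aim concerns unassisted movement. The criteria permit low-signal patients; they do not show how many there will be.

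Nor do the documents support saying that one or two such patients will decide an arm's result. That requires averaging individual percentages, which Section 10 never specifies. Stratifying by Fugl-Meyer also limits imbalance in function, though it does not balance triceps amplitude directly. Finally, the contrast between 45% and 9% depends on constant absolute error; under proportional error it disappears.

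What the reply does not answer is that Section 10 is where efficacy is defined. It omits sham, and no sentence makes the ANOVA the deciding result.

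**Conclusion.** The concern holds in a limited form. The 10% criterion is undefined, unjustified and unconnected to the planned test. If it is applied per patient, error alone meets it in about 25% of unchanged patients at an assumed CV of 10%, and 37% at 20%. Under constant error with an SD of 5 microvolts (range 3 to 10) the figures are 45% (41 to 47%) at 10 microvolts and 9% (1 to 25%) at 100 microvolts. Applied to the active arm alone, the chance runs from below 1% to 29%, depending on the assumed CV and how the mean is formed. All of these rest on assumed error, because the documents give none.

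The weakness is not confined to low-signal patients: under proportional error it applies to everyone. No bias in the planned ANOVA has been shown. This should be corrected before analysis because it settles what counts as success, and the correction is nearly free.

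**What to change.** In Section 10 and in the primary analysis line of Section 12, state efficacy as the active-minus-sham difference in triceps peak amplitude at discharge, adjusted for the patient's own baseline amplitude. Define that baseline as the mean of the two to three lead-in recordings. If a relative size is wanted, apply the 10% to the ratio of the two arms' adjusted means, not to individual or within-arm percentage changes.

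Eligibility, visits and recordings do not change. The cost is rewording one endpoint sentence and one analysis line. The small downside is that a per-patient figure for those improved by 10% is no longer the headline; it could still be described for both arms side by side.

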Preliminary clinical evidence suggests that implanted VNS augments the benefits of upper limb rehabilitation for individuals with chronic upper limb hemiparesis post-stroke. Dawson et al (2015) randomized twenty-one patients who were greater than 6 months from an ischemic stroke to receive either VNS plus rehabilitation (N=9) or upper limb rehabilitation alone (N=11). Rehabilitation intervention was intensity matched across groups, and consisted of three 2hr treatment sessions per week for 6 weeks. VNS was delivered manually by the therapist via button press while the patient completed all prescribed motor tasks. Results from the per-protocol analysis demonstrated a significant improvement in upper limb Fugl Meyer scores for the VNS plus rehabilitation group as compared with the rehabilitation group alone (between group difference= 6.5 points). There were no serious adverse device effects, though side effects included transient dysphagia and vocal fold paralysis following implantation, and temporary nausea and taste disturbances following stimulation [8]. Overall, this first clinical trial of stimulator implanted VNS suggests a promising augmentative tool may become available to enhance post-stroke motor rehabilitation. However, given that vagus nerve stimulation appears to be task-selective and dose-sensitive, refinement of stimulation parameters is still needed. Thus, we propose an investigation of specific vagus nerve stimulation timing parameters via a transcutaneous route to potentially improve intervention efficacy and decrease side effects.

For this study, investigators in the Laboratory of Rehabilitation Robotics are collaborating with investigators in the Center for Bioelectronic Medicine (CBEM) to test the hypothesis that vagus nerve stimulation via an external electrode placed on the ear and timed to deliver stimulation during upper limb extensor movements will improve the outcome in patients after stroke. Currently, CBEM investigators have experience with 8 healthy controls and 8 patients with lupus delivering transcutaneous auricular vagus nerve stimulation (tVNS) without any serious adverse events. The advantages of non-invasive tVNS device for use in stroke rehabilitation are to eliminate the need for surgical implantation, reducing untoward side effects in an already vulnerable population, and to potentially develop a clinical tool for better and more efficient functional recovery.

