11. RESEARCH PROCEDURES

- *Include a detailed description of all procedures to be performed on the research subject and the schedule for each procedure.*
- *Include any screening procedures for eligibility and/or baseline diagnostic tests*
- *Include procedures being performed to monitor subjects for safety or minimize risks*
- *Include information about drug washout periods*
- *If drugs or biologics are being administered provide information on dosing and route of administration*
- *Clearly indicate which procedures are only being conducted for research purposes.*
- *If any specimens will be used for this research, explain whether they are being collected specifically for research purposes.*
- *Describe any source records that will be used to collect data about subjects*
- *Indicate the data to be collected, including long term follow-up*

Consecutive Sessions of tVNS during robotic therapy intervention

Thirty-six patients with chronic, post-stroke upper extremity hemiparesis will be accepted into this study, and randomized to receive either sham or active tVNS treatment coupled with robotic therapy. There will be 2-3 baseline measurement periods prior to treatment. Following the lead-in period, subjects will participate in a training period consisting of approximately 1 hour sessions robotic therapy paired with tVNS 3x/week for 3 weeks, for a total of 9 sessions. Following the training period, subjects will complete clinical and objective measures both immediately at discharge and again a 3-month follow-up visit.

Lead-in Period

- Week 1, Visit 1 (approximately 90 minutes)
 - Baseline clinical outcome measures
 - Instrumental measures with EMG
 - Medical screening
 - Consent
- Week 1, Visits 2-3 (approximately 60 minutes each)
 - Baseline clinical outcome measures
 - Instrumental measures with EMG

Training Period

- Weeks 2-4, Visits 4-12 (approximately 60 minutes)
 - robotic therapy + tVNS

- Device tolerance questionnaires (every session)

Discharge Evaluation

- Week 4, Visit 13 (approximately 60 minutes)
 - Clinical outcome measures
 - Instrumental measures with EMG

Follow-Up Evaluation

- Week 16, Visit 14 (approximately 60 minutes)
 - Clinical outcome measures
 - Instrumental measures with EMG

**Phase II
Schedule**

	Screen 1	Screen 2	Screen 3	taVNS Tx + robotics	DC eval	3 mo FU
	Visit 1	Visit 2	Visit 3	Visit 4-12	Visit 13	Visit 14
Informed Consent	X					
Medical Hx	X					
Demographic Info	X					
Inclusion Criteria	X					

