15. DATA AND SAFETY MONITORING PLAN

A specific data and safety monitoring plan is only required for greater than minimal risk research. For guidance on creating this plan, please see the [Guidance Document](#) on the HRPP website.

*Part I – this part should be completed for all studies that require a DSMP.
Part II – This part should be completed when your study needs a Data and Safety Monitoring Board or Committee (DSMB/C) as part of your Data and Safety Monitoring Plan.*

Part I: Elements of the Data and Safety Monitoring Plan

- *Indicate who will perform the data and safety monitoring for this study.*
- *Justify your choice of monitor, in terms of assessed risk to the research subject's health and well being. In studies where the monitor is independent of the study staff, indicate the individual's credentials, relationship to the PI, and rationale for selection*
- *List the specific items that will be monitored for safety (e.g. adverse events, protocol compliance, etc)*
- *Indicate the frequency at which accumulated safety and data information (items listed in # above) will be reviewed by the monitor (s) or the DSMB/C.*
- *Where applicable, describe rules which will guide interruption or alteration of the study design.*
- *Where applicable, indicate dose selection procedures that will be used to minimize toxicity.*
- *Should a temporary or permanent suspension of your study occur, in addition to the IRB, indicate to whom will you report the occurrence.*

Although this is a minimal risk study, to protect both the integrity of the data and the safety of all study participants, study data review in aggregate will occur every 4 months by the Principal Investigator. Additionally, if a subject experiences an adverse event during the course of the study, the PI will be notified immediately and the IRB will be contacted within 5 days if the PI determines that the event is or may be related to the study intervention. If it is determined that the study intervention caused or may have caused the adverse event, the participant may be removed from the study and the study protocol will either be modified or ceased. However serious adverse events are unanticipated as tVNS is a nonsignificant risk device. Additionally, there were no serious adverse device effects of implanted VNS or tVNS in individuals with stroke [8, 41].

Part II: Data and Safety Monitoring Board or Committee

- *When appropriate, attach a description of the DSMB.*

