17. RISKS TO SUBJECTS

- *Describe any potential risks and discomforts to the subject (physical, psychological, social, legal, or other) and assess their likelihood and seriousness and whether side effects are reversible. Where appropriate, describe alternative treatments and procedures that might be advantageous to the subjects.*
- *Include risks to others, like sexual partners (if appropriate)*
- *Discuss why the risks to subjects are reasonable in relation to the anticipated benefits and in relation to the importance of the knowledge that may reasonably be expected to result.*
- *Describe the procedures for protecting against or minimizing any potential risks, including risks to confidentiality, and assess their likely effectiveness.*

Transcutaneous vagus nerve stimulation by the ear has the potential to cause temporary changes in hearing, pain at the site of stimulation, skin irritation or burns, and in rare occurrences, increases or decreases in heart rate as a result of activating the cervical vagus nerve via transcutaneous electrical stimulation of the ear. However, serious adverse events are unanticipated with tVNS, as there were no serious adverse device effects of implanted VNS or transcutaneous VNS in individuals with chronic stroke [8, 41].

Ear pain/discomfort occurs from stimulation of the sensory nerves innervating the ear. Activation of the sensory nerves correlates with the peak charge density applied to the innervated area. Consequently, during the stimulation period, we will monitor for discomfort and can adjust the charge intensity in real time to rapidly reduce the stimulation intensity and reduce the physical discomfort. This physical discomfort is not serious and the side effects are reversible.

Thermal burns at the stimulation site are due to excess power density through the electrode area. The FDA guidance for document for powered muscle stimulators (FDA document 2246) specifies a maximum power density at the electrode site of 250 mW/cm². The MIDI fabricated stimulator has a maximum power density of less than 100 mW/cm², which falls well below the guidance limit for thermal burns. A portable, battery-powered oscilloscope will be used to confirm peak current for the Roscoe device, and ensure that power density does not exceed this level.

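### The only safety endpoint counts serious, device-suspected events, so the mild effects the protocol foresees fall outside it, and no active-versus-sham summary of adverse events or tolerance data is planned

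*Combined protocol and SAP*

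**What the plan says.** Section 10 gives a single safety endpoint, "The primary safety endpoint will be any serious adverse events of suspected relationship with the tVNS investigational device", and names no secondary one.

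Section 17 lists what stimulation at the ear may do: "temporary changes in hearing, pain at the site of stimulation, skin irritation or burns, and in rare occurrences, increases or decreases in heart rate". Of the ear discomfort it says "This physical discomfort is not serious and the side effects are reversible". It also treats nausea, dizziness and light-headedness as symptoms to act on during a session. On serious events it says "serious adverse events are unanticipated with tVNS", and Section 15 agrees: "However serious adverse events are unanticipated as tVNS is a nonsignificant risk device".

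Section 11 lists "Device tolerance questionnaires (every session") in the training period, Visits 4 to 12. It also has the tolerated intensity found and logged before each session in every patient. For Visits 13 (discharge) and 14 (three-month follow-up) it lists clinical and EMG measures only.

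Section 12 analyses EMG peak amplitude and the Fugl-Meyer score. It does not mention adverse events, the questionnaires or the tolerance log.

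Section 15 does cover non-serious events operationally. Any adverse event goes to the principal investigator at once, those that are or may be related go to the IRB within 5 days, and the principal investigator reviews the data in aggregate every 4 months.

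**The concern.** The endpoint and the foreseen harms do not meet. The plan expects mild, temporary effects and expects no serious ones, yet only serious ones are counted. The likely safety result is therefore zero in both arms, which would tell a reader almost nothing about how well the stimulation is tolerated.

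A sham arm and nine tolerance assessments per patient are already in the design. Without a planned summary by arm, the pilot could finish with no estimate of how often active patients had ear pain, skin irritation, hearing change, dizziness or nausea compared with sham patients. A later, larger trial would want those figures.

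An analyst can still tabulate questionnaires that were collected. Answers that were never sought at Visits 13 and 14 cannot be recovered, so whether effects described as temporary did resolve may go unrecorded.

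**Working it through.** **Inputs.** Enrolment of 36, a target of at least 15 per group and dropout of 10–15% (Section 12); equal allocation (Section 11, Blinding); nine sessions (Section 11). The documents give no adverse-event rates, so every rate below is an assumption, shown over a range.

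**1. The plan's own figure.** Enrolment per arm = 15/(1 − dropout), rounded up.
- 15% dropout: 15/0.85 = 17.6, so 18 per arm, 36 in total.
- 10% dropout: 15/0.90 = 16.7, so 17 per arm, 34 in total.

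The stated 36 reproduces at the upper dropout rate. The safety data will come from 15 to 18 active patients.

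**2. What a zero would mean.** With 0 events in n patients, the one-sided 95% upper bound is 1 − 0.05^(1/n).
- n = 18: 1 − 0.05^(1/18) = 15.3%.
- n = 15: 1 − 0.05^(1/15) = 18.1%.

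**3. Chance of at least one event in the active arm.** This is 1 − (1 − p)^n.

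| Assumed risk p | n = 15 | n = 18 |
|---|---|---|
| Serious, 0.5% | 7.2% | 8.6% |
| Serious, 1% | 14.0% | 16.5% |
| Serious, 2% | 26.1% | 30.5% |
| Non-serious, 10% | 79.4% | 85.0% |
| Non-serious, 20% | 96.5% | 98.2% |
| Non-serious, 30% | 99.5% | 99.8% |

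Over the serious-event range, the stated endpoint is zero in the active arm with probability between about 69% (100 − 30.5) and 93% (100 − 7.2). Non-serious effects at 10–30% would usually be seen, but no endpoint or analysis counts them.

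**4. What a comparison by arm could deliver.** Exact power of Fisher's test, at an assumed two-sided 5% level, for 15 to 18 per arm:
- 30% versus 5%: 28–38%.
- 50% versus 10%: 54–67%.

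For 30% versus 5%, the approximate 95% half-width of the difference is 1.96 × √(0.30 × 0.70/n + 0.05 × 0.95/n). That is 23 percentage points at n = 18 and 26 at n = 15. The comparison can describe but not test.

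**5. Data planned but without an analysis.** Full attendance gives 36 × 9 = 324 session questionnaires; 30 completers give 30 × 9 = 270.

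**The case against.** The strongest reply is that this is a small pilot that the protocol classes as minimal risk, that neither Specific Aim concerns safety, and that Section 15 already routes adverse events of any severity to the principal investigator. Nothing forbids a table by arm. This stands as far as it goes: no safeguard is missing, and the gap is in the endpoint, the planned summary and the last two visits. The 15.3% bound also reflects the sample size and would apply to any event not seen in 18 patients.

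A reader might infer more than the documents support:

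- *That none of the foreseen effects could ever enter the endpoint.* Only ear discomfort is expressly called not serious, and seriousness is not defined. A severe burn or a heart-rate event judged serious and device-suspected would count.
- *That non-serious events are ignored.* Section 15 has them notified and, where related, reported. Monitoring is planned; a summary against sham is not.
- *That patients will never be asked about after-effects.* The documents show only that no question is listed at Visits 13 and 14. The schedule table is not exhaustive, since it omits the questionnaire even at Visits 4 to 12.
- *That the questionnaire already captures the named effects.* Its content is not shown.
- *That a sham comparison would test the hope in Section 3 "to potentially improve intervention efficacy and decrease side effects".* Those words follow an account of implanted stimulation, including effects of the implantation. Active versus sham does not address that contrast.

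One further caution bears on the remedy. Threshold finding precedes each session for every patient, and sham patients receive real current at the start, so ear pain or skin irritation can arise in either arm.

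**Conclusion.** The point holds in limited form and should be acted on. The single safety endpoint excludes the foreseen effects in their expected, non-serious form. Section 12 has no summary by arm of adverse events or tolerance data, and no tolerance question is listed after the last training session.

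A zero on the stated endpoint would still be compatible, at the one-sided 95% level, with a serious-event risk of up to 15.3% (18 active patients) or 18.1% (15), and it would say little about tolerability. These bounds need only the group sizes and equal allocation. The probabilities of seeing an event rest on assumed rates, though the contrast between serious and non-serious events holds over the whole range shown. The remedy is a descriptive summary, since the trial is too small for a formal test of tolerability.

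**What to change.** **Section 10.** Keep the serious-event endpoint. Add a secondary safety endpoint, for example: *all adverse events, regardless of seriousness or suspected relationship, including ear pain, skin irritation or burn, hearing change, dizziness or light-headedness, nausea, and any heart-rate event recorded as an adverse event.*

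**Section 11.**
- Confirm that the session questionnaire asks about each effect named in Section 17 that a patient can report, and add items where it does not.
- Record discomfort during threshold finding or the ramp separately from effects during the session.
- Ask the same questions at Visits 13 and 14, and record whether earlier effects have resolved.

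**Section 12.** Report the number and percentage of patients with each effect, by arm, counting each patient once per effect however many sessions are involved, with exact confidence intervals. State that this is descriptive. Report how many patients lack later data because they were withdrawn, since Section 16 ends data collection at withdrawal and allows withdrawal for a related adverse event.

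**Cost.** Protocol wording, one extra table, and a few minutes at two visits that patients already attend. The report will show some minor events where it might otherwise have shown only a zero.
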